11.1.7 Study Record Retention

Study-related records, including the regulatory file, study device accountability records, consent forms, subject source documents and electronic records, should be maintained for a period of 2 years following the date a marketing application is approved for the investigational device for the indication for which it is being investigated; or, if no application is filed or if the application is not approved for such indication, until 2 years after the investigation is discontinued and the Sponsor is notified. These documents should be retained for a longer period, however, if required by local policies or regulations. No records will be destroyed without the written consent of EmitBio.

11.1.8 Protocol Deviations

A protocol deviation is any non-compliance with the clinical trial protocol, any process that is noted in the protocol and refers to details in the protocol or GCP requirements, or any critical study procedures with specific instructions in ancillary documents referenced in the protocol.

The non-compliance may be either on the part of the subject, the participating clinical site PI, or the study site staff. Following a deviation(s), corrective actions should be developed by the site and implemented promptly. All individual protocol deviations will be addressed in study volunteer study records.

It is the responsibility of the participating clinical site PI and study staff to use continuous vigilance to identify and report deviations within five working days of identification of the protocol deviation, or within five working days of the scheduled protocol-required activity. All deviations will be kept in a log and must be promptly reported to EmitBio Inc. Protocol deviations must be sent to the IRB in accordance with the IRB reporting guidelines. The participating clinical site PI and study staff are responsible for knowing and adhering to the IRB requirements. Document protocol deviations and violations will be recorded on the case report form, as well as in the subject's chart if the deviation is subject specific.

11.1.9 Publication and Data Sharing Policy

All study data and reports of study data are the property of the study sponsor. The sponsor may grant the PI the right to publish the results of this research in a scientific journal, conditional upon the review and concurrence of the sponsor.

11.1.10 Conflict of Interest Policy

The independence of this study from any actual or perceived influence, such as by the pharmaceutical industry, is critical. Therefore, any actual conflict of interest of persons who have a role in the design, conduct, analysis, publication, or any aspect of this trial will be disclosed and managed. Furthermore, persons who have a perceived conflict of interest will be required to have such conflicts managed in a way that is appropriate to their participation in the design and conduct of this trial. EmitBio Inc requires that all study team members disclose any conflict of interest.

Clinical Study sites are required to maintain a mechanism for the management of all reported dualities of interest.

11.1.11 Research Related Injuries

For any potential research related injury, the participating clinical site PI or designee will assess the subject. Study staff will try to reduce, control and treat any complications from this trial. Immediate medical treatment may be provided by the participating clinical site, such as giving emergency medications to stop immediate allergic reactions. As needed, referrals to appropriate health care facilities will be provided to the subject. The participating clinical site PI should then determine if an injury occurred as a direct result of procedures or the device used in this trial.

If it is determined by the participating clinical site PI that an injury occurred to a subject as a direct result of the procedures or device used in this trial, then referrals to appropriate health care facilities will be provided to the subject. No financial compensation will be provided to the subject by EmitBio Inc. or the participating clinical site for any injury suffered due to participation in clinical research.

12 APPENDICES

12.1.1 RD-X19 Investigational Device Manual

12.1.2 Toxicity Grading Scale

## Statistical Analysis Plan

### 1 Purpose of Statistical Analysis Plan

The purpose of the statistical analysis plan is to describe in detail all the data, statistical methods, and summary tables required to implement the statistical analysis of Clinical Study Protocol EB-P20-01 (Section 10 in the study protocol version 5.0, dated January 17, 2021).

### 2 Study Objectives

To evaluate multiple doses of the RD-X19 treatment device and establish evidence for safety and efficacy for each of the RD-X19 doses compared to sham in SARS-CoV-2 infected individuals with outpatient COVID-19.

### 3 Study Design, Efficacy Endpoints, and Sample Size Determination

#### 3.1 Study Design

For the purpose of exploring the above objectives, the study will be conducted as a randomized, double-blind, sham-controlled dose finding study in SARS-CoV-2 infected outpatients with mild-to-moderate COVID-19.

This dose ranging portion of the study plans to enroll a minimum of 60 volunteers who are seronegative for SARS-CoV-2 Spike IgG antibody at baseline with 30 in each of at least two dosing cohorts (20 assigned to RD-X19 and 10 assigned to sham per cohort, 2:1 randomization).

Cohort A will begin with 24 J/cm^2 per treatment, administered 2X/Day for duration of 7 days. Once 80% of subjects (n=24) in Cohort A complete the Day 8 visit and no predefined safety signals as outlined in the study pausing/stopping criteria have been observed, Cohort B, 32 J/cm^2 per treatment will start enrollment. In the event device-related serious adverse events or patterns of device-related adverse events, including application site reactions, are observed in Cohort A, and based on the review and recommendation of the external safety monitoring committee (SMC) of unblinded data, the study may proceed with enrollment and dosing in Cohort C, 16 J/cm^2 per treatment in keeping with SMC recommendations. An illustration of the ascending (or descending) dose finding design is provided below.

#### **Cohort A: RD-X19 24 J/cm^2 vs. Sham**

[figure not shown]
(5 minute treatment, 2X/Day for a duration of 7 days)

#### **Cohort B: RD-X19 32 J/cm^2 vs. Sham**

(5 minute treatment, 2X/Day for a duration of 7 days)

#### **Cohort C: RD-X19 16 J/cm^2 vs. Sham**

(5 minute treatment, 2X/Day for a duration of 7 days)

During the investigation of Cohort B, once 80% of the subjects complete the Day 8 visit without observation of safety signals meeting the definition of predefined pausing/stopping criteria, a blinded review of available safety data for Cohort A and Cohort B was conducted along with a blinded assessment of the proportion of 'success' events on the first primary endpoint of sustained symptom resolution for the subjects within each Cohort. At the sponsors option, the final cohort enrollment was increased in sample size, targeting up to an additional 150 subjects (2:1 randomization). This option to increase overall enrollment is intended to provide better resolution of the point estimate between a safe, well tolerated dose and sham treatment in a broader population, including subjects who are SARS-CoV-2 Anti-Spike IgG antibody positive at baseline, either through natural infection or immunization, in preparation for future trials.

**Note:** The Cohort which has the optional additional enrollment will be considered the 'Final Cohort'. In the event that the sponsor elects to not proceed with the optional additional enrollment then the last Cohort investigated will be defined to be the 'Final Cohort'. As such, the Final Cohort is defined as the cohort including the final randomized subject.

Subjects meeting all inclusion criteria and none of the exclusion criteria will be randomized in a 2:1 ratio within each dosing cohort.

The clinic visits will occur at:

- Visit 1 / Screening, Enrollment & Randomization
- Visit 2 / Day 3
- Visit 3 / Day 5 ( $\pm 1$  day)
- Visit 4 / Day 8 ( $\pm 1$  day)
- Visit 5 / Day 14 ( $\pm 2$  day) / Early Termination (ET)

Assessments of study subjects will occur on study days 1, 3, 5, 8, with the final assessment visit on Day 14. Telephonic outreach by study personnel will occur on days 2 and 4 for additional safety monitoring and to enhance compliance with at-home study procedures. Study subjects

requiring hospitalization will be tracked until discharge or death and the date and time of these events will be captured in the study data.

#### Study Pausing Criteria

If observations of a device-related SAE or patterns of discrete or non-resolving device-related TEAEs grade 2 or higher in the same System Order Classified (SOC ) Preferred Term (PT), based on the Medical Dictionary for Regulatory Activities (MedDRA) coding, are observed in a single subject, dosing will be discontinued for that subject and observed at regularly scheduled follow up visits.

EB-P20-01 enrollment in any Cohort will be paused if any of the following events occur:

- Any subject experiences a device related SAE.
- Any subject experiences laryngospasm, bronchospasm or anaphylaxis within 2 hours after treatment.
- Two (2) or more subjects experience an allergic reaction such as generalized urticaria (defined as occurring at three or more body parts) within 72 hours after treatment.
  - Potential photoallergy or phototoxicity to one or more photosensitizing drugs in the subject's medical history should be investigated in all cases. See "Medications that Increase Sensitivity to Light: A 1990 Listing (Levine 1990)."
- Three (3) or more subjects experience a Grade 2 or higher TEAE (including local, systemic and/or clinical laboratory abnormalities), in the same SOC PT based on the Medical Dictionary for Regulatory Activities (MedDRA) coding, considered to be related to RD-X19.

While the study enrollment is paused, attribution will be determined and assigned and the SMC will be notified that a consultation is required. Given the frequency of visits and the duration of the protocol, study device use may continue in unaffected subjects within a cohort until a recommendation is provided to unpause or terminate cohort enrollment by the SMC.

The SMC, when convened by the sponsor, will not only make a recommendation to unpause enrollment or discontinue dosing in a given cohort, but will also make a recommendation to the sponsor for ascending or descending from Cohort A in the event safety/tolerability signals are observed within the first dosing cohort (24 J/cm^2 RD-X19 device).

A study volunteer may elect to discontinue participation in the trial at any time. Investigative staff will ask the volunteer to return for an early termination evaluation, but they are under no obligation to do so. All study subjects must return the RD-X19 device at study termination and study staff must verify that the device serial number matches the study subject to whom it was assigned.

#### Study Stopping Criteria

When a device-related SAE or two or more device-related severe TEAEs (grade 3) in the same SOC PT are observed within a given cohort, further enrollment and treatment in that Cohort will be discontinued.

### 3.2 Efficacy Endpoints

The primary efficacy endpoints are:

- Time to sustained resolution of COVID-19 signs and symptoms (in all subjects) as measured by the time from baseline (in hours) when cough, sore throat, nasal congestion, headache, chills and or sweats, myalgia, fatigue, and nausea (with or without vomiting) have been assessed by the subject as none (0) or mild (1) and all symptoms remain at or below 1 until the Day 14 visit. Subjects reporting a persistent fever (100.5 degrees for 36 hours or more) and/or SpO2 levels <96% with any shortness of breath are considered not to have met the success criterion on that day even if all other symptoms are reported as none (0) or mild (1).
- Time to sustained resolution of COVID-19 signs and symptoms (in subjects with mild disease at baseline) as measured by the time from baseline (in hours) when cough, sore throat, nasal congestion, headache, chills and or sweats, myalgia, fatigue, and nausea (with or without vomiting) have been assessed by the subject as none (0) or mild (1) and all symptoms remain at or below 1 until the Day 14 visit. Subjects reporting a persistent fever (100.5 degrees for 36 hours or more) and/or SpO2 levels <96% with any shortness of breath are considered not to have met the success criterion on that day even if all other symptoms are reported as none (0) or mild (1).

Note: The second primary endpoint is defined in the same way as the first primary endpoint, but is evaluated only in subjects with mild disease at baseline.

Secondary clinical endpoints:

- Proportion of study subjects who achieve 'Composite Resolution' at Day 8 defined as both a negative SARS-CoV-2 antigen test within the window for Visit 4 (Days 7 – 9) and all eight symptoms assessed by the subject as none (0) or mild (1), absence of fever and SpO2  $\geq 96\%$  without shortness of breath at study day 8 (as reported on the Diary Card Day 8-Assessment 1).
- Proportion of study subjects who experience progression of COVID-19 as defined by an increase of the composite COVID-19 severity score greater than baseline at any point in the study on or after Day 3.
- Proportion of study subjects who answer yes to either of the following patient-reported global impression assessments independently at each of the Day 8 and Day 14 visits,
  - a) In the past 24 hours, have you returned to your usual health (before your COVID-19 illness)?
  - b) In the past 24 hours, have you returned to your usual activities (before your COVID-19 illness)?
- Proportion of study subjects with any one or more of the following severe clinical outcomes (including proportions of study subjects for each individual outcome):

- 1) who require medical attention or intervention attributed to COVID-19
- 2) who progress to severe systemic illness with respiratory rate  $\geq 30$ /minute, heart rate  $\geq 125$ , O2 saturation  $\leq 93\%$  on room air or PaO2/FiO2  $\leq 300$  mm Hg, or lung infiltrates upon imaging  $>50\%$ .
- 3) who require hospitalization for severe COVID-19
- 4) who require endotracheal ventilation or ECMO with or without the use of solumedrol
- 5) who die

Secondary virologic endpoints:

- Mean change in nasopharyngeal viral load on days 3, 5, 8, and 14
- Geometric mean nasopharyngeal viral load at baseline and on days 3, 5, 8, and 14
- Proportion of subjects demonstrating clearance of viral infection, defined as a negative nasopharyngeal swab via RT-qPCR as assessed on Days 3, 5, 8 and 14

Exploratory assessments of effects of RD-X19 in saliva viral load include:

- Mean change in saliva viral load on days 3, 5, 8, and 14
- Geometric mean saliva viral load at baseline and on days 3, 5, 8, and 14

Exploratory assessment of effects of RD-X19 in oral microbiome includes:

- Change in  $\alpha$  and  $\beta$  diversity in microbial flora from baseline on day 8 and day 14 as analyzed by 16S rRNA subunit analysis from frozen saliva samples

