6.1 Inclusion Criteria

A subject must meet all the following criteria to be eligible for **inclusion** in this study:

1. Positive for SARS-CoV-2 as detected using an FDA authorized SARS-CoV-2 antigen test at or within 24 hours of the screening visit.
2. COVID-19 signs and symptoms within 72 hours from symptom onset, including at least two moderate* or greater symptoms from: cough, sore throat, nasal congestion, headache, unexplained chills and/or sweats, myalgia, fatigue, nausea (with or without vomiting).
 - Subjects with the presence of at least one moderate symptom and either a) a fever with an oral temperature of at least 100.5 °F or b) shortness of breath/difficulty breathing on exertion (e.g., walking, going up and down stairs) are also eligible for enrollment.

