| Secondary Clinical Outcome Assessments | |
| 
Day 8 Composite Resolution | 
Proportion of study subjects who achieve 'Day 8 Composite Resolution' is defined as both a negative SARS-CoV-2 antigen test within the window for Visit 4 and all symptoms assessed by the subject as none (0) or mild (1), absence of fever and SpO₂ ≥96% without shortness of breath on study day 8. |

| | |
|--|--|
| 
• Worsening of Disease• Return to Pre-COVID Health• Severe Clinical Outcomes | 
• Number and percentage of study subjects who experience progression of COVID-19 as defined by an increase of the composite COVID-19 severity score greater than baseline at any point in the study on or after day 3.• Numbers and percentages of study subjects on day 8 and day 14 who answer Yes to the following patient-reported global impression assessments, a) return to usual health and b) return to usual activities.
a) In the past 24 hours, have you returned to your usual health (before your COVID-19 illness)? Yes or Nob) In the past 24 hours, have you returned to your usual activities (before your COVID-19 illness)? Yes or No• Numbers and percentages of study subjects who:
1) who require medical attention or intervention attributed to COVID-19;2) who progress to severe disease with respiratory rate >30/minute and/or O2 saturation <94% on room air or FiO2 ≥300% with any respiratory distress;3) who require hospitalization for severe COVID-19;4) who require endotracheal ventilation or ECMO with or without the use of solumedrol; and5) who die. |
| Secondary Virologic Outcome Assessments | |
| 
• Change in Nasopharyngeal VL | 
• Mean change in nasopharyngeal VL from baseline on days 3, 5, 8, and 14.• Tabulated geometric mean |

| | |
|---------------------------------------|---|
| | 
nasopharyngeal VL at baseline and on Days 3, 5, 8 and 14.
 
• Clearance of viral shedding (undetectable SARS-CoV-2 VL) |
| 
Exploratory Assessments
 | |

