- Scenario 3: For Day x (pm), if severity is missing for all 8 symptoms, the diary entries from the previous completed entry, either Day x (am) or Day x-1 (pm), will be carried forward for Day x (pm). For Day x (am), if severity is missing for all 8 symptoms, the diary entries from the previous completed entry, either Day x-1 (pm) or Day x-1 (am) will be carried forward for Day x (am). Same applied to fever and SpO2 level/shortness of breath.
- Scenario 4: For Day x assessment y where all 8 symptoms are scored 0 or 1, if fever or SpO2 level is missing, subject’s success or failure for Day x assessment y will be determined in the same way as in Scenario 2.

For derivation of the primary efficacy endpoints, subjects who were hospitalized due to COVID-19 will be designated as treatment failures, and right censored at 384 hours (16 days), i.e., censored at the end of the Visit 5 window.

For subjects who discontinued the study early for any reason other than hospitalization for COVID-19, only diary data up to subject’s discontinuation date will be used. For derivation of the primary efficacy endpoints such subjects will be considered censored at the time of their last assessment.

**Note:** Subjects discontinuing for any reason are ineligible to meet the success criteria on either primary efficacy endpoint because "success" requires the conditions to be met until the Day 14 visit.

The COVID-19 Composite Severity Score (CSS) at baseline is defined as the sum of the eight individual COVID-19 signs and symptoms severity scores divided by eight. For purposes of calculating the COVID-19 composite severity score in the secondary endpoint of worsening disease from baseline, subjects with missing diary card entries (reporting none of eight symptoms scored) will not be considered to have met the criteria for worsening of disease at that assessment timepoint. Subjects with incomplete diary card entries (reporting from 1 to 7 of the eight symptoms scored), will be handled by dividing the sum of all scores reported by the number of scores reported, and compared to the baseline CSS.

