	-- n (%) subjects who require hospitalization for severe COVID-19	XX (XX.X)	XX (XX.X)	XX (XX.X)	XX (XX.X)
	-- n (%) subjects who require endotracheal ventilation or ECMO	XX (XX.X)	XX (XX.X)	XX (XX.X)	XX (XX.X)
	-- n (%) subjects who die	XX (XX.X)	XX (XX.X)	XX (XX.X)	XX (XX.X)
Modified Full Analysis Set					
	N	XX	XX	XX	XX
	n (%) Subjects who experience progression of COVID-19 	XX (XX.X)	XX (XX.X)	XX (XX.X)	XX (XX.X)
	n (%) Subjects with severe clinical outcomes (at least one of following)	XX (XX.X)	XX (XX.X)	XX (XX.X)	XX (XX.X)
	-- n (%) subjects who require medical attention or intervention attributed to COVID-19	XX (XX.X)	XX (XX.X)	XX (XX.X)	XX (XX.X)
	-- n (%) subjects who progress to severe disease 	XX (XX.X)	XX (XX.X)	XX (XX.X)	XX (XX.X)
	-- n (%) subjects who require hospitalization for severe COVID-19	XX (XX.X)	XX (XX.X)	XX (XX.X)	XX (XX.X)
	-- n (%) subjects who require endotracheal ventilation or ECMO	XX (XX.X)	XX (XX.X)	XX (XX.X)	XX (XX.X)
	-- n (%) subjects who die	XX (XX.X)	XX (XX.X)	XX (XX.X)	XX (XX.X)
Per Protocol Population					
	N	XX	XX	XX	XX
	n (%) Subjects who experience progression of COVID-19 	XX (XX.X)	XX (XX.X)	XX (XX.X)	XX (XX.X)
	n (%) Subjects with severe clinical outcomes (at least one of following)	XX (XX.X)	XX (XX.X)	XX (XX.X)	XX (XX.X)
	-- n (%) subjects who require medical attention or intervention attributed to COVID-19	XX (XX.X)	XX (XX.X)	XX (XX.X)	XX (XX.X)
	-- n (%) subjects who progress to severe disease 	XX (XX.X)	XX (XX.X)	XX (XX.X)	XX (XX.X)
	-- n (%) subjects who require hospitalization for severe COVID-19	XX (XX.X)	XX (XX.X)	XX (XX.X)	XX (XX.X)
	-- n (%) subjects who require endotracheal ventilation or ECMO	XX (XX.X)	XX (XX.X)	XX (XX.X)	XX (XX.X)
	-- n (%) subjects who die	XX (XX.X)	XX (XX.X)	XX (XX.X)	XX (XX.X)

[1]: Progression of COVID-19 is defined by increase of composite COVID-19 severity score (> baseline score) at any point in the study on or after Day 3.

[2]: Subjects will be designated as Severe having any one of the following: Respiratory Rate  $\geq 30$ , Heart Rate  $\geq 125$ , SpO2  $\leq 93\%$ , or lung infiltrates upon imaging  $>50\%$ .

EmitBio Inc.  
Protocol: EB-P20-01  
SAP Version: 2.0

Source: Listing 16.x.x  
O:\Studies\EmitBio\EB-P20-01\Biometrics\Programs\Tables\xxx.sas ran on Month Day, Year at hh:mm on data from Month Day, Year.

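### The progression endpoint has no severity floor, so for subjects with a baseline score below 1.0 an all-mild card can count as COVID-19 progression; separately, partly completed cards are averaged on a different base from baseline.

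*SAP*

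**What the plan says.** From Day 3 onward, SAP 3.2 counts "progression of COVID-19 as defined by an increase of the composite COVID-19 severity score greater than baseline at any point in the study". Protocol 6.4 gives the same rule ("increase of the composite COVID-19 severity score greater than baseline at any point in the study on or after day 3"), and it is repeated in Protocol 4.1.2 Table 1, 9.2 and 9.3. The footnote to SAP Table 14.2.2.3 states the comparison to be programmed: "Progression of COVID-19 is defined by increase of composite COVID-19 severity score (> baseline score". None of these places sets a minimum rise, a confirming card, or an exemption for cards on which no symptom exceeds mild.

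SAP 5.2.1 defines the baseline composite as the "sum of the eight individual COVID-19 signs and symptoms severity scores divided by eight". Later cards with one to seven answers "will be handled by dividing the sum of all scores reported by the number of scores reported, and compared to the baseline CSS". A card with no answers "will not be considered to have met the criteria for worsening of disease at that assessment timepoint".

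The entry rule in Protocol 6.1 fixes how low the baseline can be: "including at least two moderate* or greater symptoms from: cough, sore throat, nasal congestion, headache" and four further symptoms. One moderate symptom plus fever or exertional shortness of breath also suffices.

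For the primary endpoint, a card meets the symptom criterion when all eight items are 0 or 1. Scenario 2 of SAP 5.2.1 scores blanks as 0 when every answered item is 0 or 1.

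**The concern.** There are two separate problems.

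The first concerns complete cards. The primary endpoint looks at the worst item on the card, while progression looks at the mean of all items. Someone who enters with a few moderate symptoms and moves to a wider spread of mild ones can exceed the baseline mean on a card where nothing is worse than mild. That card is favourable for the primary endpoint and adverse for this one.

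The second concerns partly completed cards. The later score is a mean over the items answered and the baseline is normally a mean over eight. The comparison therefore depends on which items were left blank as well as on how the subject feels.

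SAP Table 14.2.2.3 reports the result for the FAS, mFAS and PP populations, beside severe clinical outcomes and under the label of COVID-19 progression. No test is planned, so the tabulated percentage is the whole result. Readers will take it as clinical deterioration.

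**Working it through.** The plan states no expected rate or power for this endpoint, so there is no figure to reproduce. The check enumerates the scoring rules.

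**Lowest eligible baseline (Protocol 6.1).**
- Two moderate symptoms, the rest absent: (2 + 2)/8 = 0.50.
- One moderate symptom plus fever or exertional dyspnoea: 2/8 = 0.25.

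**Complete cards with every item 0 or 1.** With k mild symptoms the score is k/8, and progression needs k/8 > baseline.

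| Baseline | Fewest mild symptoms counted as progression | Card score |
|---|---|---|
| 0.25 | 3 | 0.375 |
| 0.50 | 5 | 0.625 |
| 0.75 | 7 | 0.875 |
| 0.875 | 8 | 1.0 |
| 1.0 or more | none | – |

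Such a card cannot score above 8/8 = 1.0, so the overlap disappears once baseline reaches 1.0.

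**Partial cards with every answered item 0 or 1.** With n items answered (n = 1 to 7) and k of them mild, the score is k/n. There are 2 + 3 + … + 8 = 35 possible (k, n) pairs. At baseline 0.50, 16 pairs exceed baseline. In 10 of the 16, k/8 does not exceed 0.50, so they count only because of the answered-items denominator. These are counts of patterns, not probabilities. In the simplest case, one item is answered and scored 1. For progression the score is 1/1 = 1.0 > 0.50. For the primary endpoint the seven blanks become 0 and the symptom criterion is met (on that basis the mean would be 1/8 = 0.125).

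**Partial cards with a moderate item.** Take baseline 12/8 = 1.50 and a later card on which only cough is answered, scored 2. The score is 2/1 = 2.0 > 1.50, so the subject has progressed. If cough was already 2 at baseline, nothing recorded has worsened. This problem is not limited to baselines below 1.0.

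**Any-card rule, illustration only.** Two cards a day over Days 3 to 14 give 2 × 12 = 24 cards. Assume an independent chance q per card of exceeding baseline without true worsening. The chance of at least one such card is 1 − (1 − q)^24:
- q = 1%: 21%
- q = 2%: 38%
- q = 5%: 71%

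Requiring two consecutive cards gives at most 23q² = 0.23%, 0.92% and 5.75%; calculated directly, 0.2%, 0.9% and 5.4%. Neither q nor independence comes from the documents.

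**The case against.** The definition is explicit and is repeated consistently in both documents. The endpoint is secondary, SAP 5.5.2 summarises it descriptively, and Protocol 10.1 confines hypothesis testing to the two primary endpoints. Total burden and worst symptom are different constructs, and going from two symptoms to five is a rise in burden by one reasonable reading. Worsening to moderate or more is captured as a TEAE under Protocol 9.2.1, and severe outcomes are tabulated separately. Reminders and payment tied to up-to-date diaries should limit blanks. The footnote to SAP Table 14.1.3 prorates baseline in the same way when baseline items are missing.

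Much of this stands. It limits the consequence, and it means the current definition deserves to stay visible. It does not answer the mismatch on partial cards: prorating an incomplete baseline does not put a complete baseline and an incomplete later card on the same items.

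Four stronger readings are tempting and are not supported:
- A reader might infer that one card can satisfy the whole primary endpoint. It cannot, because that endpoint needs all symptoms to stay at or below 1 until the Day 14 visit and has fever and SpO2/shortness-of-breath conditions. Only the symptom criterion is met on the card.
- A reader might blame averaging over answered items for the overlap. The 5/8 example is a complete card, so partial-card averaging widens the overlap but does not create it.
- A reader might infer that the proportion will be high in both arms. The 21%, 38% and 71% rest on assumed rates. Scores from one person are likely to be correlated, and the independence assumption flatters a two-card rule.
- A reader might treat progression and later resolution in one subject as a contradiction. A subject can worsen and then recover; the difficulty is that both labels can attach to the same card.

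**Conclusion.** The point holds in two parts. For subjects with baseline below 1.0, a complete card with every item 0 or 1 can be counted as progression while meeting the primary symptom criterion. For any baseline low enough to be exceeded by the answered items, a card with one to seven answers can be counted as progression because its mean is taken over different items from the baseline mean.

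Both follow from the stated rules without assumptions about data. Their frequency does not: the documents give neither the distribution of baseline scores nor the rate of partial cards. The most that can be said is that the proportion may be inflated in both arms and harder to interpret as deterioration. Type 1 error and the power statements are unaffected. The change is worth making because it is cheap and the descriptive percentage is all that will be reported.

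**What to change.** 1. In SAP 5.2.1, for cards with one to seven answers, compare the sum of the answered items with the baseline sum of the same items, using only items scored at both times. The cough example then counts only if cough itself rose.
2. In SAP 3.2 and Table 14.2.2.3, report progression with the added condition that at least one symptom on that card is grade 2 or higher, and show the current definition beside it. Protocol 9.2.1 already uses a moderate-or-greater threshold for symptom worsening. This change is needed as well as the first: on same-item comparison, a card whose only answer rose from 0 to 1 would still exceed baseline.
3. Optionally, add a sensitivity line requiring two consecutive cards. Count a single card above baseline as confirmed if it is followed by COVID-19 hospitalisation, withdrawal or no further diary entries. Without that provision the line would lose subjects who worsen and then stop reporting, which is why it should not be the main definition.

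The wording should be aligned in Protocol 4.1.2 Table 1, 6.4, 9.2 and 9.3, and settled before unblinding. The cost is a small derivation change and extra table lines, with no new data. The downside is that rises made up only of mild symptoms appear only in the current-definition line.
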